The investigator will offer to answer any questions the Subject may have. If the Subject agrees to participate in the investigation, then the Subject must sign and date the IPC form prior to the day of surgery. However, if the IPC is signed on the day of surgery, then the source document must state that the Subject was given adequate time prior to the time of surgery to review and give consent. In such a case, the time the Subject signed the IPC form must be documented.

The original IPC form remains with the clinical investigator (i.e., within the CRF booklet or clinic chart) and a copy is provided to the Subject. The IPC is not forwarded to the Sponsor. Instead, the Investigator will complete the "Assurance of Investigator" form documenting that informed consent has been properly obtained and then submit a copy to the Sponsor. Once a Subject has executed the IPC documentation, they are considered a study Subject.

Post-operative visit schedule will consist of the following: pre-op, operative, and post-operatively at 2 weeks, 4-6 weeks, 3 months, 6-months, 12-months, 24 months and 60 months.

Time

2 weeks (7-21 days)

Data Collected

Average Pain Score (VAS)

Amount of pain MED use/day

Walking Distance

Use of Assistive Device

IIS Clinical Research Agreement
[name]
January 28, 2013

4-6 weeks (22-45 days)	Average Pain Score (VAS) Average pain MED use/day Walking distance Assistive Device X-ray Protocol cup position stem position limb length offset Return to work/Activity/Driving Timed Walking Test Harris Hip Score HOOS
3 months (60-120 days)	Pain Score (VAS) Average pain MED use/day Walking distance Assisted device Timed Walking Test Harris Hip Score HOOS
6 months (130-240 days)	Average Pain Score (VAS) Harris Hip Score HOOS
12 months (270-425 days)	Average Pain Score (VAS) Harris Hip Score X-ray Protocol HOOS
24 months (426-1460)	Average Pain Score (VAS) Harris Hip Score X-ray Protocol
60 months (1461-2737)	Average Pain Score (VAS) Harris Hip Score X-ray Protocol

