6.0 Statistical **Methodology**

Treatment Assignment

Treatment assignment will be determined with the use of a randomization schedule that will utilize blocks to ensure approximate treatment balance at any time during the study enrollment phase.

Sample Size Determination

Sample size was determined with the use of historical unpublished data of Harris Hip parameters at 6 weeks post-operatively from patients who underwent the primary THA using the anterior surgical approach. The percentage of patients at 6 week post-operative that had the ability to climb stairs normally, and walk unlimited, were 37%, and 40% respectively. Using a 2-tailed Fisher's Exact test and assuming a difference in clinical results of 30% and statistical power of 85% the required sample size for this study is 40 patients per treatment group. To account for 10% attrition the sample size was increased to 44 patients per treatment group (88 patients total).

Primary Endpoint

The proportion of patients with the ability to climb stairs normally or walk unlimited at 6 weeks post-operatively is the primary endpoint in this study. However, the HOOS patient self-assessment dimensions of Pain, Symptoms, Activities of Daily Living, Sport & Recreation, and Quality of Life will be important secondary endpoints. Six minute walk test distances and VAS Pain scores are also secondary endpoints

Analysis Populations

The Intent-to-Treat population will be analyzed.

Interim Analyses

No formal interim analyses will be conducted.

Analyses Planned

Demographics of the 2 treatment groups and pre-operative Harris Hip Evaluation sub-scores and HOOS sub-scores will be compared using appropriate statistical methodologies to determine comparability of treatment groups pre-operatively.

The proportion of patients able to climb stairs normally or walk unlimited as evaluated with the Harris Hip Evaluation at 6 weeks post-operatively will be compared using a 2-tailed Fisher's Exact test. Potentially covariates (e.g. age, BMI, gender) will be assessed using logistic regression techniques.

IIS Clinical Research Agreement
[name]
January 28, 2013

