HOOS sub-scores of Pain, Symptoms, Activities of Daily Living, Sport & Recreation, and Quality of Life will be scored according to the HOOS Users Guide and will be compared using parametric or non-parametric techniques (as appropriate) at 6 weeks, 3, 6 and 12 months post-operatively to determine if there is a difference between treatment groups and at what time points the difference are detected.

Six minute walk test distances at 6 weeks and 3 months and VAS Pain scores will also be compared using parametric or non-parametric techniques (as appropriate) at 6 weeks, 3, 6, 12 months, 24 months and 60 months post-operatively to determine if there is a difference between treatment groups and at what time points the difference are detected.

The prevalence of both inter-operative and post-operative complications and adverse events such as dislocation, hospital re-admission, revision operation, and other postoperative events not normally associated with THA will be compared between groups using a Fisher's Exact (2-tailed) test, with $p \leq 0.05$ being considered significant.

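### The 2-week VAS pain score is collected but has no planned comparison, and the HOOS and walk-distance comparisons name no adjustment for pre-operative values

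*Combined protocol and SAP*

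**What the plan says.** Section 6.0 (Primary Endpoint) calls the five HOOS dimensions important secondary endpoints and adds: "Six minute walk test distances and VAS Pain scores are also secondary endpoints". It sets no limit there on the VAS time points.

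Section 6.0 (Analyses Planned) then gives the comparison times:
- HOOS sub-scores "will be compared using parametric or non-parametric techniques (as appropriate) at 6 weeks, 3, 6 and 12 months post-operatively".
- For the other two outcomes, "Six minute walk test distances at 6 weeks and 3 months and VAS Pain scores will also be compared". On the VAS times, the same sentence states that these ratings "will also be compared using parametric or non-parametric techniques (as appropriate) at 6 weeks, 3, 6, 12 months, 24 months and 60 months".
- The purpose in both cases is "to determine if there is a difference between treatment groups and at what time points the difference are detected".

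The visit schedule at the end of Section 5.0 has seven follow-up visits: 2 weeks, 4-6 weeks, and 3, 6, 12, 24 and 60 months. VAS pain is listed at all seven, and at 2 weeks it is the first item. HOOS and the timed walking test first appear at 4-6 weeks.

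On pre-operative data, Section 5.1 lists a timed walking test but neither HOOS nor VAS. Section 6.0 nevertheless says that "pre-operative Harris Hip Evaluation sub-scores and HOOS sub-scores will be compared" between the groups, which implies that HOOS is collected before surgery. Covariates are mentioned only for the primary endpoint, through logistic regression.

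**The concern.** Section 2.0 gives the primary focus as short-term safety, efficacy and return to function. VAS is the only named secondary endpoint measured at 2 weeks, so leaving that visit out means that no named secondary endpoint has a planned comparison before the 4-6 week visit. If the arms differ in early pain, the plan as written either does not test it or makes the test an unplanned one, which carries less weight.

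The second part concerns efficiency. Patients will differ in hip function before surgery, and with about 40 per arm a chance imbalance in the pre-operative score can blur or mimic a group difference afterwards. The plan uses pre-operative HOOS to check that the groups are comparable, but does not say that it will be used in the comparison itself.

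**Working it through.** **Plan's own figure.** The plan gives no figure for the secondary comparisons. Its only sample-size figure, 40 per group, belongs to the primary endpoint. It reproduces with a two-tailed Fisher's exact test at an assumed 0.05 for 40% against 10% (power 85.2%). It is used here only as the number per arm.

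**Collected against compared.** Collection times are from the Section 5.0 schedule, comparison times from Section 6.0. The 4-6 week visit is taken as the 6-week analysis.

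| Outcome | Visits collected | Visits compared | Left out |
|---|---|---|---|
| HOOS | 4-6 weeks; 3, 6, 12 months | 6 weeks; 3, 6, 12 months | none |
| Walk test | 4-6 weeks; 3 months | 6 weeks; 3 months | none |
| VAS pain | 2 weeks; 4-6 weeks; 3, 6, 12, 24, 60 months | 6 weeks; 3, 6, 12, 24, 60 months | 2 weeks |

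One of seven VAS assessments is omitted. For the other two outcomes the lists agree fully. The walk row assumes that the timed walking test is the six-minute walk test; the matching visits support this.

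**Number of comparisons.**
- HOOS 5 × 4 = 20, VAS 6, walk 2: total 28. With 2-week VAS: 29.
- Expected false positives if no difference exists and each is tested at 0.05: 28 × 0.05 = 1.4; 29 × 0.05 = 1.45. The 0.05 is assumed, since the plan states it only for complications. The expectation does not require independent tests.

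**What a marginal result looks like.** Two-sample t test, 40 per arm, 78 degrees of freedom; difference in SD units = t × √(2/40).
- p = 0.05: 1.991 × 0.2236 = 0.445 SD.
- p = 0.05/28 = 0.00179: 3.235 × 0.2236 = 0.723 SD.

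A difference between about 0.45 and 0.72 SD at one visit alone is therefore marginal evidence (36 per arm: 0.470 to 0.766; 44 per arm: 0.424 to 0.687). The upper limit is an illustrative Bonferroni level, not a rule in the plan.

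**Gain from pre-operative adjustment (HOOS, walk).** With N = 80 and correlation r between pre- and post-operative values, the variance of the adjusted difference relative to the unadjusted one is (1 − r²) × (N − 3)/(N − 4) = (1 − r²) × 77/76. The documents give no r.
- r = 0.1: 0.99 × 77/76 = 1.003
- r = 0.3: 0.91 × 77/76 = 0.922
- r = 0.5: 0.75 × 77/76 = 0.760
- r = 0.7: 0.51 × 77/76 = 0.517

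**Gain from a mixed model for VAS.** Take a fraction m missing the 60-month visit only, known covariance, and six earlier VAS visits. The variance relative to using attenders only is 1 − m × R², where R² is the share of 60-month variance explained by the earlier visits.
- Equal correlation ρ: R² = 6ρ²/(1 + 5ρ) = 0.216, 0.429, 0.653 for ρ = 0.3, 0.5, 0.7.
- First-order autoregressive: R² = ρ² = 0.090, 0.250, 0.490.
- At m = 0.1 (the plan's attrition figure, applied here to 60 months): 0.978, 0.957, 0.935 and 0.991, 0.975, 0.951.

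The reduction is about 1% to 7%.

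**The case against.** The strongest reply is that collecting a measure does not oblige anyone to test it. Section 1.0 treats the early post-operative period as lasting up to 5 years, the primary endpoint is at 6 weeks, and the planned comparison of complications already covers the first weeks. This stands in part: the early period is not wholly unexamined, and the omission may be deliberate. But no reason is given, and every other scheduled VAS visit has a comparison.

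A reader might go further and infer that visit-by-visit tests are invalid here and that a repeated-measures model is required. The documents do not support that. Separate between-arm comparisons at each visit are valid in a randomized two-arm trial, answer the stated question about time points directly, and use every patient seen at that visit. With complete data, a VAS model with no baseline term, categorical visits and a full treatment-by-visit term returns the same per-visit mean differences. It does not reduce the number of comparisons either. The plan's wording does not exclude a longitudinal model or baseline adjustment; it names neither.

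A reader might also infer that 28 comparisons make the secondary results misleading. The plan has one primary endpoint with a named test, labels the rest secondary, and does not say that it will present them as confirmed.

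**Conclusion.** The point holds and is minor. It is a matter of record that one of seven scheduled VAS assessments, the earliest, is outside the planned comparisons while VAS is a named secondary endpoint. It is also a matter of record that no adjustment for pre-operative values is named for HOOS or walk distance.

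The value of adjustment rests on an assumed correlation: a variance reduction of about 8% to 48% for correlations of 0.3 to 0.7, and none at 0.1. It also rests on two readings of the protocol: that HOOS is collected before surgery, as Section 6.0 implies but Section 5.1 does not list, and that the pre-operative timed walking test is the six-minute walk test. No pre-operative VAS is listed, so this gain is not available for VAS. There, a mixed model is optional, worth roughly 1% to 7% of variance at 60 months under the assumptions shown.

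The primary endpoint, its test and the sample size are not affected.

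**What to change.** 1. In Section 6.0, add 2 weeks to the VAS comparison times. If the omission is intended, say so and state that the 2-week score will be descriptive only.
2. In Section 6.0, state that each HOOS sub-score and walk distance will be compared at each listed visit adjusted for its pre-operative value. Use either ANCOVA at each visit or one mixed model per outcome with treatment, visit, treatment-by-visit and the pre-operative value. Choose between them before the outcome data are examined. Report per-visit differences with 95% confidence intervals.
3. List HOOS in Section 5.1 if it is collected before surgery, and state whether the timed walking test is the six-minute walk test.
4. State that an isolated marginal difference at a single visit will be read as exploratory.

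The cost is a few sentences and slightly more programming. No extra visits or patients are needed, and no new data provided that pre-operative HOOS is already collected. There is one more secondary comparison, 29 instead of 28, which adds 0.05 to the expected false positives on the assumption above.

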The second surgical technique used in the study will be the posterior approach. This approach uses a standard OR table with the patient placed in the lateral decubitus position. A 12-14cm skin incision is utilized over the posterior-lateral corner of the hip. The gluteus maximus muscle is split in line with its fibers and the posterior capsule is opened. The hip is dislocated posteriorly and a femoral neck osteotomy is performed. The acetabular and femoral components are inserted in the same manner as is done with the anterior approach with press-fit fixation utilized. The posterior approach is well described in all major texts on Orthopedic Surgery. To minimize selection bias the surgical technique will be determined by a randomization schedule.

Radiographs and clinical data will be gathered for each qualifying patient in the manner outlined in the Study Procedures below. Harris Hip Evaluation scoring will be used to evaluate pain, function, activity levels, deformity, and range of motion. The HOOS patient reported outcomes will be used to evaluate function and pain relief.

Deaths, device, and procedure related complications will be reported.

Data to be collected includes, but is not limited to that specified in Section 5.2 below.

The primary focus of the study is to compare the short-term safety, efficacy and return to function of patients undergoing primary total hip arthroplasty utilizing an anterior approach vs a posterior approach. Upon completion of the study, a summary of the results will be submitted for publication.

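### Safety is part of the study's primary focus, but its only planned between-group analysis is a Fisher test at 0.05 with no effect estimate or interval, and 44 patients per arm give that test little power for uncommon events

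*Combined protocol and SAP*

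**What the plan says.** Section 2.0 (Overview) states: "The primary focus of the study is to compare the short-term safety, efficacy and return to function of patients", followed by the two approaches being compared. The same section also promises that "Deaths, device, and procedure related complications will be reported".

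Section 6.0 (Analyses Planned) gives safety one sentence. The quantity is "The prevalence of both inter-operative and post-operative complications", extended to "adverse events such as dislocation, hospital re-admission, revision operation, and other postoperative events not normally associated with THA". These "will be compared between groups using a Fisher's Exact (2-tailed) test", with significance declared at p of 0.05 or below. The sentence names no risk difference, ratio or confidence interval. It gives no follow-up window, although visits run to 60 months. It does not say whether the unit is a patient or an event, or whether event types are tested singly or pooled.

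Section 6.0 (Sample Size Determination) bases the trial on 6-week function only: Fisher's exact test, a 30-point difference and 85% power give 40 per arm, raised to 44 for attrition. No event rate, margin or power is stated for safety.

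**The concern.** A trial sized for a 30-point difference in a common functional outcome will see few dislocations, revisions or re-admissions. If the planned comparison ends in a significance verdict, that verdict will usually be non-significant for such events, even when the true rates differ by an amount surgeons would care about. With no planned estimate or interval, the report need not show which differences the data exclude and which they leave open. Results are to be submitted for publication, so the risk is that a non-significant p-value stands as the trial's whole comparative safety statement.

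**Working it through.** **Inputs from Section 6.0.** Two-sided Fisher's exact test; threshold 0.05 for safety; 44 per arm enrolled, 40 after attrition. No complication rates are given, so every rate used for power below is an assumption.

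**1. The plan's own figure.** Exact enumeration of Fisher's test, two-sided 0.05 (alpha is not stated for the primary endpoint, so 0.05 is assumed), for 40% v 10%: the smallest n with at least 85% power is 40 per arm (85.2%). This matches the plan, and 40 × 1.1 = 44. The match is for a 30-point fall from the anterior rate; for 70% v 40% the same method needs 52 per arm. Nothing below depends on that.

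**2. What the safety rule needs (no assumption about rates).** With x events in one arm and none in the other, at 44 per arm, two-sided p = 2 × C(44, x) / C(88, x).
- x = 3: 2 × 13,244 / 109,736 = 0.24
- x = 5: 2 × 1,086,008 / 39,175,752 = 0.055
- x = 6: 2 × 7,059,052 / 541,931,236 = 0.026

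So 5/44 (11.4%) against 0/44 is not significant, and 6/44 (13.6%) against 0/44 is the first split that is. With one event in the smaller arm, 7 v 1 gives p = 0.058 and 8 v 1 gives 0.030. At 40 per arm, 6 v 0 is still the minimum.

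**3. Power under assumed rates.** Power is the sum, over all pairs (a, b) with Fisher p ≤ 0.05, of Bin(a; 44, p1) × Bin(b; 44, p2).

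| Assumed true rates | Power at 44 per arm |
|---|---|
| 5% v 1% | 1.4% |
| 10% v 5% | 5.4% |
| 10% v 2% | 14% |
| 20% v 10% | 17% |
| 15% v 5% | 22% |
| 20% v 5% | 47% |
| 30% v 10% | 56% |
| 40% v 10% | 88% |

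At 40 per arm the first and third rows fall to 1.0% and 11%. For 80% power at 44 per arm, the higher rate must be about 20% against 1%, 28.5% against 5%, or 37% against 10%.

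**4. What an interval would show.** Take 3/44 v 0/44 (p = 0.24). The Wilson 95% limits are 2.35% to 18.22% and 0% to 8.03%; the difference is 6.82 points. Newcombe limits:
- lower: 6.82 − √[(6.82 − 2.35)² + (8.03 − 0)²] = 6.82 − 9.19 = −2.4 points
- upper: 6.82 + √[(18.22 − 6.82)² + 0²] = 18.2 points

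The p-value alone gives one label; the interval shows that an excess of up to about 18 points is not excluded. For a single arm with no events, the exact two-sided upper 95% limit is 1 − 0.025^(1/44) = 8.0%.

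**The case against.** The case for leaving the plan alone has four parts.

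- **Safety is not the primary endpoint.** The documents set no safety hypothesis or margin, and low power for uncommon harms is normal in a trial sized on function. This stands. Neither the sample size nor Fisher's test, which is valid for sparse counts, is an error.
- **The plan offers more than a label.** It compares prevalence, which implies per-arm proportions, and Section 2.0 promises that complications will be reported. This also stands, and it narrows the gap to a missing between-group estimate with an interval, a window and a counting unit.
- **An interval adds no information on rare harms.** True: the 3 v 0 example remains inconclusive. But it shows how inconclusive, which the p-value does not.
- **The power figures rest on assumed rates.** True for power; the thresholds of 5 v 0 and 6 v 0 do not.

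A reader might also infer from the phrase "other postoperative events not normally associated with THA" that expected complications drop out of the comparison. The text does not support this well. The phrase qualifies only the last item of an open, illustrative list that expressly names dislocation, and the governing term is complications and adverse events generally. The wording is clumsy, but the point does not rest on it.

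**Conclusion.** The point holds in a limited form. An aim named in Section 2.0 is analysed only by a significance rule with no effect estimate or interval. At 44 per arm that rule has about 1% to 14% power for individual events at assumed rates of 1% to 5% in one arm and 5% to 10% in the other. It is adequate only for very large pooled differences: 88% at 40% v 10%, but 56% at 30% v 10%.

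Two stronger readings are tempting and not supported. One is that significance can almost never be reached, so the trial cannot answer its safety question. That depends on event rates the documents do not give, and it fails for a common pooled complication rate with a large difference. The other is that the plan will treat non-significance as equal safety. No section says so; it is a risk of interpretation that the plan leaves open. The change is worth making because it is cheap and bears on a stated aim. The primary endpoint is unaffected.

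**What to change.** In Section 6.0, replace the safety sentence with wording to this effect:

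> For any complication, and separately for dislocation, hospital re-admission, revision and other events, the number of patients with at least one event (n/N) will be given per arm, with the anterior-minus-posterior risk difference and its 95% confidence interval (Newcombe or exact), over [stated follow-up window]. Two-sided Fisher p-values will be supportive. A p-value above 0.05 will not be reported as similar safety.

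The sponsor should choose the window, fitted to the existing visit schedule, before the data are compared by arm. Tying the event wording to the complications recorded under Sections 5.2 and 5.3 is an optional editorial clarification.

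Cost: a few lines of text and some table columns, with no new patients and no new data. The drawback is that the safety statement will look less certain, because the intervals will be wide.
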